2. STUDY DESIGN

Study design: Single-blind study. Patients will be randomized, to LLTS versus sham procedure, and remain blinded to their treatment allocation. Both treatment options will utilize similar equipment, namely the use of alligator clips which will be placed on the tragus and earlobe of the right ear for patients (see Appendix A, Figure 2). The distinction is only that in patients assigned to LLTS, they will be initiated on therapy at the time of device placement.

Prior to cardiac surgery, the discomfort threshold of both left and right tragus stimulation will be determined for all participating patients. Intermittent electrode signals, or microcurrents, are delivered at 20 Hz with 200 μ sec pulse width with variable microampere (mA) output. The discomfort threshold is defined as the stimulation intensity in mA at which point patients experience discomfort. The stimulation intensity used in the study will be set just below the discomfort threshold, as established from prior work.¹⁵ The clip will then be placed on the patient's ear at the end of surgery. After surgery is completed, the clip will then be removed and replaced on the contralateral ear. Stimulation will then continue, one ear alternating with the other, every 4 hours for a total of 48 hours. It is possible that the threshold can change during the post-operative period. If the patient shows any sign of discomfort from stimulation, the intensity of stimulation will be reduced to a level at which signs of discomfort disappears.

Follow-up will be performed with 14-day event monitor (i.e. Zio patch or CardioNet event monitor) at the time of discharge.

Electrocardiography (i.e. ECG) will be performed pre-procedure and prior to hospital discharge. Echocardiography will be assessed prior to study initiation and when clinically available in follow-up.

Duration of study: 1 month

Primary endpoints: A combination of clinical and electrocardiographic endpoints will be prospectively studied. These include:

- **Clinical:** Primary clinical endpoint is time to inpatient AF (length of stay >5 days). Secondary endpoint is any occurrence of AF during 14 day post procedure monitoring.
- **Electrocardiographic:** Arrhythmia occurrence (i.e., AF, nonsustained VT, VT or VF requiring device therapy) will be documented throughout the study period

Primary safety endpoint: Procedure-related complications will be assessed prospectively both acutely and throughout the study period, including:

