6. STATISTICAL PLAN AND CONSIDERATIONS

Primary Outcome:

1. Time to the first episode of AF >30 seconds during inpatient admission or within 14-day monitoring period

- a. In hospital: full-disclosure telemetry
- b. Time to AF will be assessed by physicians blinded to randomization
- 2. Extended hospitalization of >5 days

Secondary Outcomes:

- 1. Overall AF burden, as assessed by 2 week monitor (CardioNet or Zio Patch) upon discharge
- 2. Inflammatory markers: C-reactive protein (ordered if clinically indicated)
- 3. Actionable AF: antiarrhythmic use (including rate-control meds), CDV, anticoagulation, use of inotropes for BP support during AF
- 4. Stroke or transient ischemic attack (TIA)
- 5. All cause of mortality

Sample size estimation:

Assuming a two-armed study with composite endpoint of occurrence of AF or >5 days hospitalization, whereby the treatment group will have 50% likelihood of the event occurring and a control group will have 20% likelihood of the event occurring, as well as a 10% dropout rate, we will be able to detect differences in 80 patients (40 in each arm). Under these assumptions and using two-sided Z-Test with unpooled variance to compare the changes between these two groups, we will have 80% power ($\alpha=0.05$) to detect a difference between the group proportions of 0.30. PASS software Version 15 (NCSS, LLC, Kaysville, UT) was used to calculate the statistical power.

Statistical methods:

Patients will be studied based on the randomization allocation. Patients who refuse to continue with study treatment (i.e. they refuse to wear ear clip) during time of therapy will be analyzed as intention-to-treat per allocation group. Fisher's exact or the Chi-Square test will be used for categorical variables, and continuous parameters will be compared by the two-tailed unpaired Student's t test and the F test for analysis of variance (ANOVA), as needed. Kaplan-Meier method will be used for computing the event free survival curves. Each strategy will be compared within this cohort of patients for its impact on percent incidence of POAF and length of stay. Multiple logistic regression and multiple regressions using the Cox proportional hazards model will be performed to determine the independent association of each of the demographic variables with clinical outcome.

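### An AF-free death in hospital within the first 5 days is scored as no event in the composite and as a short stay, because the plan gives no rule for death

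*Combined protocol and SAP*

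**What the plan says.** All of the following is in the Combined protocol and SAP.

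- **Section 6, Sample size estimation:** the endpoint is a "composite endpoint of occurrence of AF or >5 days hospitalization". It has two components, and death is not one of them.
- **Section 6, Primary Outcome:** two items are listed. The first is "Time to the first episode of AF >30 seconds during inpatient admission or within 14-day monitoring period". The second is "Extended hospitalization of >5 days", with no exception for a stay ended by death.
- **Section 2, Study design:** the primary clinical endpoint again names only AF and a stay over 5 days.
- **Section 6, Secondary Outcomes:** item 5 is "All cause of mortality". Section 8 also lists death among the adverse effects to be documented.
- **Section 6, Statistical methods:** the strategies are compared for their "impact on percent incidence of POAF and length of stay". The only patients given a handling rule are those who refuse the ear clip; they stay in their allocated group. The 10% dropout allowance does not mention deaths.

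**The concern.** Take a patient who dies on postoperative day 2 without AF. The AF component is no, and the stay over 5 days is no. The composite is therefore no event, and the length-of-stay comparison receives a very short, favourable value. A patient discharged well on day 4 without AF gets the same composite score.

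This flatters whichever arm the death occurs in. Deaths should be few, but there are only 40 patients per arm, so a single patient can matter when the result lies near the significance boundary. The population is cardiac surgical and the plan itself lists death among its outcomes, so the case is foreseeable.

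**Working it through.** **1. The plan's own figure.** Inputs from section 6: event rates 0.50 and 0.20, two-sided alpha 0.05, 80% power, unpooled Z-test, 10% dropout.

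n per arm = (1.960 + 0.842)² × (0.5×0.5 + 0.2×0.8) / 0.30² = 35.76, rounded up to 36. With dropout, 36 / 0.9 = 40 per arm, or 80 in total. The stated N reproduces.

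**2. Naming the arms.** Section 6 prints "the treatment group will have 50% likelihood of the event occurring" and "a control group will have 20% likelihood of the event occurring", which is opposite to the hypothesis of benefit. The arms are therefore named by rate below. N is symmetric in the two rates, so step 1 is unaffected.

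**3. How likely is such a death?** The documents give no figure. Assume operative mortality of 1 to 3%, with a quarter to a half of those deaths AF-free and by day 5:

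- lower end: 1% × 0.25 = 0.25%
- upper end: 3% × 0.5 = 1.5%
- chance of at least one among 80 = 1 − (1 − q)^80, which is 1 − 0.9975^80 = 18% at the lower end and 1 − 0.985^80 = 70% at the upper end

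**4. What one such death does to the verdict.** Draw event counts from Binomial(n, 0.5) and Binomial(n, 0.2). Apply Fisher's exact test at 0.05, add events to one arm, and sum the probability of all pairs of counts whose verdict changes. Fisher's test is one of the two that section 6 names for categorical variables.

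| Recoded as events | n = 36 per arm | n = 40 per arm | Direction |
|---|---|---|---|
| 1 in the 20% arm | 10.8% | 9.0% | significance lost |
| 1 in the 50% arm | 7.6% | 6.7% | significance gained |
| 2 in the 20% arm | 22.4% | 18.9% | significance lost |
| 2 in the 50% arm | 13.9% | 12.2% | significance gained |

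These figures are conditional on such deaths having occurred.

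**5. Combining steps 3 and 4.** For one death, 0.18 × 0.067 = 1.2% and 0.70 × 0.108 = 7.6%. That is roughly 1 to 8% of trials.

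**6. At the planned rates exactly.** With 20/40 against 8/40, Fisher p = 0.009. Rescoring deaths in the lower-rate arm gives 0.019 (9/40), 0.037 (10/40) and 0.066 (11/40). Three are needed before significance is lost.

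**7. Effect on power if death is counted.** Suppose both rates rise equally by q and the difference stays 0.30. Power at 36 per arm is Φ(0.30 / √[(p₁(1−p₁) + p₂(1−p₂))/36] − 1.96). It is 0.803 at q = 0, 0.797 at q = 1% and 0.792 at q = 2%.

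**The case against.** **The plan never says that such a patient is a success.** A reader might infer that this is a stated rule. It is not: the score follows from a literal reading of the definition where the plan is silent on death. An analyst could instead call the death a dropout, treat it as missing, or censor it. This stands as a limit on the wording, but it does not remove the problem. The written definition gives the bad score, nothing overrides it, and several choices left open after the fact are a reason to fix one in advance.

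**The first primary outcome is different.** A reader might extend the point to time to AF. The documents do not support that. Section 6 plans Kaplan-Meier curves, where the usual default is to censor at death, not to count a success. Censoring has its own weakness, since death precludes AF, but that is a separate matter. The composite itself appears only in the sample-size paragraph, so its role in the final analysis is unclear.

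**The size is easily overstated.** At an assumed mortality of 1 to 3%, the chance of any death among 80 is 55 to 91%. That is not the relevant probability, because only AF-free in-hospital deaths by day 5 matter. Section 3 excludes urgent and emergency cases and requires a life expectancy of at least 1 year, which argues against the upper end. This stands.

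**Deaths are not hidden.** Mortality is a secondary outcome, and adverse events are reviewed at midpoint. This is true, but it does not correct the primary score.

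**Adding death changes the target.** This is fair, and it is why a version without death should be kept as a sensitivity analysis.

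**Conclusion.** The point holds for the composite, the 5-day outcome and the length-of-stay comparison. As defined, each scores an AF-free in-hospital death during a stay of 5 days or less as favourable. It is a minor defect: a missing rule whose literal default misclassifies the patient.

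The expected effect is small. It depends on an early death rate that the documents do not give, on the planning rates of 50% and 20%, and on Fisher's test. A reader might conclude that one death would usually decide the trial, or that the sample size is wrong. Neither follows: a single recoded death changes the verdict in about one trial in ten at most, and the stated 80 reproduces.

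**What to change.** Before unblinding, that is, before any outcome is tabulated by arm, state in section 6:

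- In-hospital death during a stay of 5 days or less counts as an event for the composite and for the 5-day outcome. This wording covers death on day 5 itself.
- In-hospital death takes the worst rank in the length-of-stay comparison. That comparison then has to be rank-based; the planned t-test cannot carry a worst rank.
- For time to AF, death is a competing event, reported as cumulative incidence.
- The composite without death is reported as a sensitivity analysis.

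The cost is a few sentences. Deaths are already collected. The downside is that the composite becomes slightly broader than AF and stay, with a loss of about one point of power if 2% of patients in each arm die this way (0.803 to 0.792).

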7. RISKS AND BENEFITS

Risks:

LLTS is a novel, entirely noninvasive means to stimulate the auricular branch of the vagus nerve. There are risks associated with alligator clip application which will be similar in the two groups; these risks include discomfort to the tragus or skin abrasion. There is discomfort with high level stimulation, and at the time of neuromodulation, strict attention to patient comfort will be maintained.

Benefits:

There are significant possible benefits to this treatment. Should LLTS be effective at reducing postoperative AF, this would be associated with significant benefit to the patient as well as potentially lead to a significant improvement in overall postoperative management of patients.

8. SAFETY AND ADVERSE EVENTS

Safety:

As noted above, periprocedural complications will be logged with respect to procedure, system-related, and lead-related events. All complications will be independently reviewed at the midpoint by the primary investigator (PI). Should there be a trend towards increased complication risk, the study will be halted.

Adverse Events:

As noted above, all adverse events associated with devices will be monitored periprocedurally and continuously through the study. The PI will independently review all events after randomization of 20 subjects in order to make a determination for continuance.

Adverse Effect Documentation:

1. Sinus bradycardia or AVB after stimulation
2. Discomfort or possible skin abrasion due to tragus stimulation
3. Major organ-system failure
4. Death

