REFERENCE THERAPY	The reference therapy will be a sham control group; i.e., patients on whom an LLTS device with a non-functioning electrode will be applied and in whom therapy will not be delivered.
STATISTICAL METHODOLOGY	Traditional statistical methods will be employed. The student's T-test will be used for continuous comparisons. Fisher's exact or the Chi-square test will be applied for dichotomous variables. Time to endpoint analysis will be performed using the Kaplan-Meier method.

LIST OF ABBREVIATIONS

AAD	ANTIARRHYTHMIC DRUG THERAPY
ACE-I	ANGIOTENSIN-CONVERTING ENZYME INHIBITOR
AF	ATRIAL FIBRILLATION
ARB	ANGIOTENSIN RECEPTOR BLOCKER
BB	BETA-BLOCKER
CABG	CORONARY ARTERY BYPASS GRAFT
CRT	CARDIAC RESYNCHRONIZATION THERAPY
FDA	FOOD AND DRUG ADMINISTRATION
GDMT	GOAL-DIRECTED MEDICAL THERAPY
HF	HEART FAILURE
ICD	IMPLANTABLE CARDIOVERTER-DEFIBRILLATOR
IRB	INSTITUTIONAL REVIEW BOARD
LBBB	LEFT BUNDLE-BRANCH BLOCK
LV	LEFT VENTRICULAR
LLTS	LOW-LEVEL TRAGUS STIMULATION
LVEF	LEFT VENTRICULAR EJECTION FRACTION
NYHA	NEW YORK HEART ASSOCIATION
POAF	POSTOPERATIVE ATRIAL FIBRILLATION
POD	POSTOPERATIVE DAY
RA	RIGHT ATRIUM
RV	RIGHT VENTRICLE
SR	SINUS RHYTHM
TTE	TRANSTHORACIC ECHOCARDIOGRAM
UCMC	UNIVERSITY OF CHICAGO MEDICAL CENTER
UofC	UNIVERSITY OF CHICAGO
VT	VENTRICULAR TACHYCARDIA
VF	VENTRICULAR FIBRILLATION

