10. STUDY MONITORING, AUDITING AND INSPECTING

All periprocedural complications and adverse events will be reviewed by the PI at study midpoint to ensure there is no significant difference in event rate between the study groups. Should there be significant differences, or if there should be a high overall event-rate out-of-line with the procedural norm for AF, the study will be halted.

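### Two of the four adverse effects in Section 8 are worded by stimulation, so events risk being recorded more often in the LLTS arm and feeding a comparison that can halt the study

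*Combined protocol and SAP*

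**What the plan says.** The Adverse Effect Documentation list in Section 8 has four items. Two are tied to stimulation: "Sinus bradycardia or AVB after stimulation" and "Discomfort or possible skin abrasion due to tragus stimulation". The other two, "Major organ-system failure" and death, apply to either arm as worded. For bradycardia/AV block the section gives no rate or degree, no time window and no starting point for a sham patient. The same section states that "all adverse events associated with devices will be monitored periprocedurally and continuously through the study", without a rule for deciding what counts as associated.

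The Study Summary describes the sham group as "patients on whom an LLTS device with a non-functioning electrode will be applied and in whom therapy will not be delivered". Section 7 says of the clip: "There are risks associated with alligator clip application which will be similar in the two groups".

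Under Section 10 the PI reviews all periprocedural complications and adverse events at the midpoint "to ensure there is no significant difference in event rate between the study groups". A significant difference halts the study. Section 8 adds a halt for a trend towards more complications and a review after 20 patients are randomized. Neither section names a test, a significance level or a boundary.

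On blinding, Section 2 describes a single-blind design in which patients are unaware of their allocation. Section 5 has the operating physician told the allocation. The only blinded assessment stated is for time to AF, in Section 6.

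**The concern.** An adverse-event definition that is to be compared between arms should be one that a patient in either arm can meet in the same way. Item 1 is not worded like that. After surgery, when most such events would be looked for, a sham patient has had no study stimulation for the event to follow. A coordinator who takes the item at its word could log bradycardia in an LLTS patient and leave the same finding unlogged in a sham patient. Item 2 has the same difficulty: it attributes abrasion to stimulation, while Section 7 attributes it to the clip, which both arms wear.

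If bradycardia or AV block occurs at some background rate without stimulation, uneven recording adds background events to the LLTS count and loses some from the sham count. The plan states no blinded assessment of adverse events that would correct this. Two things are at stake: a possible halt for an apparent harm that the device did not cause, and a final comparison of cardiac rhythm events that is hard to interpret.

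**Working it through.** **Size of the comparison.** Section 6 gives event rates of 0.50 and 0.20, a two-sided unpooled Z-test at 0.05, 80% power and 10% dropout.

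n per arm = (1.960 + 0.842)² × [0.50 × 0.50 + 0.20 × 0.80] / 0.30² = 7.85 × 0.41 / 0.09 = 35.8, so 36. Allowing for dropout, 36 / 0.90 = 40 per arm, or 80 in total.

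The plan's figure reproduces. The midpoint is taken as 40 patients, about 20 per arm. The Section 8 look at 20 patients has about 10 per arm.

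**Assumptions, none given in the documents.**
- The true rate of bradycardia/AV block, r, is the same in both arms; range 5% to 40%.
- The halting test is a two-sided Fisher exact test at 0.05.
- The test is applied to this item alone.
- A fraction s of sham events is recorded; all LLTS events are.

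**Smallest result that is significant against zero sham events.** With n per arm, the two-sided Fisher p for x v 0 is 2 × C(n, x) / C(2n, x).
- 20 per arm, 5 v 0: 2 × 15,504 / 658,008 = 0.047. For 4 v 0: 2 × 4,845 / 91,390 = 0.106.
- 10 per arm, 5 v 0: 2 × 252 / 15,504 = 0.033. For 4 v 0: 2 × 210 / 4,845 = 0.087.

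**Chance of a false significant difference.** Sum Bin(a; n, r) × Bin(b; n, s·r) over all pairs (a, b) with Fisher p < 0.05. With s = 0 this reduces to P(X ≥ 5). For example, at r = 20% and n = 20: 1 − (0.0115 + 0.0576 + 0.1369 + 0.2054 + 0.2182) = 0.370.

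Midpoint, 20 per arm:

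| True rate, both arms | No sham events counted | Half counted | Counted alike |
|---|---|---|---|
| 5% | 0.3% | 0.2% | 0.2% |
| 10% | 4.3% | 1.7% | 1.2% |
| 15% | 17.0% | 4.4% | 2.0% |
| 20% | 37.0% | 7.2% | 2.3% |
| 30% | 76.2% | 12.4% | 2.5% |
| 40% | 94.9% | 19.2% | 2.4% |

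At the 20-patient look (10 per arm) with no sham events counted, the chance is 0.2%, 3.3% and 15.0% for rates of 10%, 20% and 30%.

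At 40 per arm, the size of the final comparison, counting half of sham events gives 4.3%, 16.2% and 28.1% for the same rates, against 1.7%, 2.8% and 2.8% when both arms are counted alike.

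**The case against.** A reader might infer that sham patients cannot have these events under the plan, and that the halting comparison is therefore biased. The documents do not support that.

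- Nothing says that bradycardia or AV block in a sham patient is to be left out. Section 10 covers all adverse events, Section 5 keeps every patient on telemetry throughout the stay, and the schedule in Appendix C has one adverse-event row for the whole trial.
- Sham patients do receive some stimulation, since "the discomfort threshold of both left and right tragus stimulation will be determined for all participating patients". This is brief and before surgery, so it does not give item 1 a usable common starting point, but it does defeat a claim that the wording excludes them altogether.
- The phrase about events associated with devices does not depend on arm, because sham patients wear a device. Its weakness is the missing attribution rule.
- Only the operating physician is named as knowing the allocation. The documents do not say whether the coordinators who record data know it, so how staff would attribute events is conjecture.
- The primary safety endpoint in Section 2 (pain, abrasion, bruising) has no stimulation condition, and the Section 10 comparison also includes death and organ failure. A halt need not rest on bradycardia/AV block.
- The large percentages need almost no recording in the sham arm. At a 10% background rate even that extreme gives 4.3%, below the nominal 5%.

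All of this stands, and it limits the point to a risk. It does not remove the risk: Section 8 is the only place that describes these events, two of its items use stimulation wording, and no instruction tells staff how to apply them to sham.

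**Conclusion.** The point holds as a risk of differential ascertainment that would inflate the LLTS event rate. It is not a demonstrated bias. Its size depends on two quantities that the documents do not give: the background rate of bradycardia/AV block and the share of sham events that would be recorded. It also depends on an assumed Fisher test at 0.05 applied to this item alone. If half of sham events are recorded and the background rate is 20%, the chance of a false significant difference at the midpoint is about three times what it would be with equal recording (7.2% against 2.3%). The risk is small at background rates of 10% or below and becomes severe only when the background rate is about 15% or more and sham recording is close to nil. The calculation does not cover the Section 8 trend criterion, which has no threshold; the missing boundary for both halting rules is a separate gap. The wording should be corrected because the correction is cheap and the counts can stop the study.

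**What to change.** - Define items 1 and 2 identically in both arms: onset after application of the active or sham clip, over the same fixed-length window, whatever the suspected cause. The 48-hour application period is one such window. A window ending at discharge should be avoided, because stay beyond 5 days is itself an outcome and observation time could then differ between arms.
- Give bradycardia/AV block one prespecified definition, chosen by the trial's clinicians.
- Record suspected relationship to the device as a separate field, and do not make it a condition for collecting the event.
- Have the physicians who already assess telemetry for AF without knowledge of allocation classify bradycardia/AV block as well.
- Keep the Section 10 review on all adverse events, with these arm-neutral counts included.

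The cost is a wording amendment, one added data field and slightly more work in the telemetry read. More background events will be logged in both arms.
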